## LIST OF ABBREVIATIONS

AE	adverse event
C3	complement component 3
C4	complement component 4
CRF	case report form
CRO	Contract Research Organization
eCRF	Electronic case report form
ELISA	enzyme-linked immunosorbant assay
FDA	Food and Drug Administration
G6PD	glucose-6-phosphate dehydrogenase
GCP	Good Clinical Practice
IC	informed consent
ICH	International Conference on Harmonisation
i.v.	intravenous(ly)
IR	infusion reaction
IRB	Institutional Review Board
ITT	Intent to Treat
kDa	kilodalton
MedDRA	Medical Dictionary for Regulatory Activities
MMRM	mixed-effect model repeated measure
NIAID/FANN	National Institute of Allergy and Infectious Disease/Food Allergy and Anaphylaxis Network
NSAID	non-steroidal anti-inflammatory drug
PEG	polyethylene glycol
po	[per os] by mouth
PUA	plasma uric acid
SAE	serious adverse event
SAP	statistical analysis plan
Savient	Savient Pharmaceuticals, Inc.
SOP	standard operating procedure
SUA	serum uric acid
US	United States

## PROTOCOL SYNOPSIS

Name of product	KRYSTEXXA® (pegloticase)
Drug substance:	Pegloticase is a uric acid-specific enzyme which is a polyethylene-glycol conjugated (PEGylated) product that consists of recombinant, modified, mammalian urate oxidase (uricase) produced by a genetically modified strain of Escherichia coli . Uricase is covalently conjugated to monomethoxypoly(ethylene glycol) (mPEG; 10 kDa molecular weight). The cDNA coding for uricase is based on mammalian sequences. Each uricase subunit has a molecular weight of approximately 34 kilodaltons (kDa). The average molecular weight of pegloticase (tetrameric enzyme conjugated to a mean of 10.2 mPEG molecules) is approximately 540 kDa.
Protocol number:	M0401
Study title:	Observational study of the use of KRYSTEXXA® (pegloticase) in adult hyperuricemic patients with gout refractory to conventional therapy
Phase:	4
Objectives:	
Primary:
 
To evaluate the frequency and severity of infusion reactions (IRs), anaphylaxis, and immune complex-related events.
 
Secondary:
 
To identify serious adverse events (SAEs) associated with KRYSTEXXA therapy.
 
To further evaluate the efficacy of KRYSTEXXA in this patient population of adult hyperuricemic patients with gout refractory to conventional therapy.

Study design:	This is a multicenter, open-label, single-arm observational study.
Investigational plan:	Approximately 1500 patients will be enrolled in order to observe treatment of up to 500 patients for a duration of 1 year. Patients who discontinue treatment before 51 weeks will be asked to remain in the study for follow-up assessments for the remainder of their planned treatment duration. The number of patients to be enrolled will be reassessed approximately 2 years after the first patient is enrolled. The study will be conducted at approximately 300 centers in the United States (US). It is estimated that approximately 2.5 years will be required for recruitment, from the first to the last patient's screening visit.

---

Treatment:	Patients eligible for initial treatment with KRYSTEXXA 8 mg by intravenous (i.v.) infusion every 2 weeks will be offered enrollment into the observational study for a year. Serum uric acid (SUA) levels will be monitored prior to infusion and therapy will be discontinued if levels increase above 6 mg/dL on two consecutive measurements. If the SUA is noted to be above 6 mg/dL the sponsor suggests that a repeat SUA should be drawn when the result is noted to confirm, and if the 2 consecutive levels are noted to be above 6 mg/dL then it is advised to discontinue therapy.
Study duration:	Approximately 63 weeks, including 51 weeks of treatment and 12 weeks of follow-up.
• Selection criteria	
Inclusion criteria:
 

• Adult patients (age <math>\geq</math> 18 years) with chronic gout refractory to conventional therapy, defined as patients who have failed to normalize SUA and whose signs and symptoms are inadequately controlled with xanthine oxidase inhibitors at the maximum medically appropriate dose, or for whom these drugs are contraindicated.

• Patients who have made the decision, along with their treating physician, to begin treatment with KRYSTEXXA.

• Patients who are willing and able to give informed consent and adhere to visit/protocol schedules (informed consent must be given before the first study procedure is performed).

 
Exclusion criteria:
 

• Glucose-6-phosphate dehydrogenase (G6PD) deficiency

• Non-compensated congestive heart failure

• Pregnancy or breast feeding

• Prior treatment with pegloticase or another recombinant uricase

• Known allergy to urate oxidase

• Prior treatment or concomitant therapy with a polyethylene glycol (PEG)-conjugated drug

• Recipient of an investigational drug within 4 weeks prior to study drug administration or plans to take an investigational agent during the study

Investigational drug:	None
Reference therapy:	KRYSTEXXA® (pegloticase) 8 mg i.v. every 2 weeks

---

Efficacy criteria:	Normalization of SUA to < 6 mg/dL  Decrease in the number of swollen joints and the number of tender joints  Decrease in the frequency of gout flares  Reduction in the number of tophi
Safety criteria:	IRs, anaphylaxis, and immune complex-related adverse events, serious adverse events and adverse event profile, including gout flares
Statistical methods:	
Descriptive statistics will be employed to summarize the proportion of responders, where a responder is defined as a patient whose SUA values were < 6 mg/dL at their final 2 consecutive study visits. Descriptive statistics will be provided for the number of swollen joints and tender joints at baseline, 6 months and 12 months or Early Discontinuation; for changes in numbers of gout flares based on patient reported history at 6-week intervals for Months 1-3 and 3-month intervals thereafter; and for change in the number of tophi at 6 months (Visit 13) and 12 months (Visit 26) or Early Discontinuation.
 
It is anticipated that there may be a considerable number of study patients who will drop out of the study. The sponsor will make every effort to identify the reason(s) for dropout before reaching the primary safety endpoint. For the analysis of each efficacy endpoint, various sensitivity analyses will be performed under different assumptions of potentially informative dropouts. For continuous efficacy variables, sensitivity analyses will be performed using standard mixed-effect model repeated measure (MMRM) methods. All the analyses will be summarized using 95% confidence interval estimates. The resulting summarized statistics for efficacy will be compared to those reported from the pre-approval phase 3 studies.
 
Adverse events will be summarized by presenting the proportion of patients having any adverse event (AE), overall and by body system, and by event as defined by the Medical Dictionary for Regulatory Activities (MedDRA) preferred term. Separate summary tables will be provided for IRs, anaphylaxis AEs, and immune complex-related AEs.
 
For each type of the primary safety endpoints, one event, at most, will be counted per patient. The 95% (exact) confidence interval estimates for each type of safety endpoint will be reported for the rate of incidence both at the administrative interim analysis, for evaluating the feasibility of the study, and at the final analysis. The following hypothesis will be specifically tested: the rate of IRs seen in the phase 3 studies will be reduced in this study by monitoring SUA prior to infusions and

discontinuing therapy in patients if levels increase to above 6 mg/dL, particularly when 2 consecutive levels above 6 mg/dL are observed. With at least 500 patients enrolled with 1 year follow-up, the power of detecting a 26% IR rate (the observed value from the pre-approval phase 3 studies) against 13% is at least 90%. The rate of IRs reported during the study will be reported and compared descriptively to the rates observed in the pre-approval phase 3 studies.

There is no planned interim analysis. However, the number of enrolled patients will be reassessed approximately 2 years after the first patient is enrolled. This data will be utilized to make a prediction concerning the future enrollment profile. The enrollment goal may be adjusted depending on the drop-out rate such that approximately 500 patients will complete the 1 year treatment period.

**Assessments:** Baseline samples for identification of antibodies to pegloticase and to PEG, and determination of complement markers (complement component 3 [C3] and complement component 4 [C4]) and tryptase levels. Antibody samples at End-of-Study and at 3-month intervals during follow-up after discontinuation of treatment.

Review of concurrent medications, co-morbidities, and compliance with premedication regimes for gout flares.

Determination of SUA before each infusion.

Recording of drug, dose and timing of IR prophylactic medications.

Recording of infusion start and finish times, sodium chloride diluent used and the total volume infused.

Swollen joint and tender joint counts, and number of tophi to be assessed at baseline, 6 months (Visit 13) and 12 months (Visit 26) or Early Discontinuation.

Flares:

- At baseline, document the history of gout flares from the previous 6 months
- Documentation of the occurrence and duration of any gout flares experienced while the patient is participating in the study

IRs and anaphylaxis:

- Documentation of signs and symptoms and onset time in relation to the initiation of the KRYSTEXXA infusion, and treatment, if any
- Follow-up laboratory assessments may include the collection of samples for analysis of antibodies to pegloticase and PEG, anti-pegloticase IgE, C3, C4, and tryptase levels.

Immune complex disease:

- Clinical investigation of a presumptive immune complex disease (as per clinical practice) and of complement markers (C3, C4) will be pursued.

## **1 INTRODUCTION**

### **1.1 Disease Background**

Gout is a disease resulting from the body's inflammatory response to urate crystals that deposit in tissues and joint spaces in susceptible individuals with chronic hyperuricemia (Dalbeth and Haskard, 2005). Uric acid, the end metabolite of purine metabolism in humans, is poorly soluble in serum at concentrations above 6.8 mg/dL. Most mammals, with the exception of humans, have an endogenous intracellular hepatic uricase that converts uric acid into allantoin, a highly soluble and easily excreted end metabolite (Wu et al, 1992). Uric acid production and excretion are normally balanced in the human body, maintaining a serum concentration below the limit of urate solubility. However, this balance may be disturbed by decreased excretion, overproduction, or a combination of these factors leading to hyperuricemia (Kanellis et al, 2006). Hyperuricemia itself is not associated with symptoms or signs of disease but in the context of gout, prolonged hyperuricemia leads to precipitation of monosodium urate crystals in and around joints and other tissues and the evolution of defining clinical manifestations. The hallmark symptoms of gout are related to acute inflammatory monoarticular arthritis, lasting days or weeks and causing exquisite pain, i.e., an acute gout flare. Protracted hyperuricemia may lead not only to frequent gout flares, but may result in urate nephropathy and renal calculi, and gout tophi (nodular deposits of urate crystals and inflammatory cells) in joints, soft tissues, bones, and in some organs. The cornerstone of gout therapy is treatment of hyperuricemia with urate-lowering drugs (Becker and Jolly, 2005).

Refractory gout occurs in a subset of symptomatic gout patients whose hyperuricemia cannot be controlled with conventional xanthine oxidase inhibitors at the maximum medically appropriate dose. The hyperuricemia of most gout patients can be controlled successfully with a xanthine oxidase inhibitor (e.g., allopurinol) to reduce uric acid formation or agents such as probenecid that promote uric acid excretion (uricosuric drugs). Although failure of patient compliance in the daily use of allopurinol or uricosuric drugs is often the root cause of treatment failure (Stamp et al, 2000), allopurinol therapy at a maximum medically appropriate dose is sometimes ineffective in normalizing the serum uric acid (SUA), or may be contraindicated in patients with impaired renal function or in patients with allopurinol hypersensitivity (Hande et al, 1984; Singer and Wallace, 1986; and Arellano and Sacristan, 1993). Uncontrolled or inadequately controlled hyperuricemia leads to increasing frequency and severity of gout-related symptoms and chronic disease, e.g., gout flares, tophi, gouty arthritis, and urate nephropathy. Chronic gout may lead to joint destruction and disability. For these individuals, no effective therapies have been available to normalize the circulating uric acid as a means of slowing or reversing the progress of the disease.

### **1.2 KRYSTEXXA Background**

KRYSTEXXA® (pegloticase) is indicated for the treatment of chronic gout in adult patients refractory to conventional therapy. KRYSTEXXA is a uric acid-specific enzyme which is a

polyethylene glycol -conjugated (PEGylated) product that consists of recombinant, modified, mammalian urate oxidase (uricase) produced by a genetically modified strain of *Escherichia coli*. Uricase is covalently conjugated to monomethoxypoly(ethylene glycol) (mPEG; 10 kDa molecular weight). KRYSTEXXA achieves its therapeutic affect by catalyzing the oxidation of uric acid to the much more soluble allantoin, thereby lowering SUA with allantoin readily eliminated, primarily by renal excretion.

Additional background concerning KRYSTEXXA can be found in the current version of the Food and Drug Administration (FDA)-approved KRYSTEXXA Full Prescribing Information.

### **1.2.1 Efficacy Assessments in Clinical Studies of KRYSTEXXA**

The safety and efficacy of KRYSTEXXA® (pegloticase) has been evaluated in 7 clinical studies, including 2 replicate, multicenter, randomized double-blind, placebo-controlled studies of 6-month duration. In the two placebo-controlled studies, adult patients with chronic gout refractory to conventional therapy were randomized to receive intravenous (i.v.) infusions of KRYSTEXXA 8 mg every 2 weeks or every 4 weeks or placebo in a 2:2:1 ratio. All patients also received prophylaxis for infusion reactions (IRs) and for gout flares. To assess the efficacy of KRYSTEXXA in lowering uric acid, the primary endpoint in both trials was the proportion of patients who achieved plasma uric acid (PUA) less than 6 mg/dL for at least 80% of the time during Month 3 and Month 6. A greater proportion of patients treated with KRYSTEXXA every 2 weeks achieved urate lowering to below 6 mg/dL than patients receiving placebo (38% to 47% of patients receiving KRYSTEXXA vs. 0% of patients receiving placebo). In addition, at Month 6, the percentage of patients who achieved a complete resolution of tophi (defined as 100% resolution of at least 1 target tophus, the appearance of no new tophi, and no single tophus showed progression) was 45%, 26% and 8% with KRYSTEXXA 8 mg every 2 weeks, KRYSTEXXA 8 mg every 4 weeks, and placebo, respectively. Although the 4 week regimen also demonstrated efficacy for the primary endpoint, this regimen was associated with an increased frequency of IRs and was less efficacious with respect to tophi. Therefore, pegloticase 8 mg every 2 weeks was approved by the US FDA on September 14, 2010 for the treatment of adult patients with chronic gout refractory to conventional therapy.

### **1.2.2 Safety Assessments in Clinical Studies of KRYSTEXXA**

The most commonly reported serious adverse reactions from the pre-marketing controlled clinical trials in patients treated with KRYSTEXXA 8 mg every 2 weeks were gout flare, IR, and anaphylaxis.

Gout flares were more frequent during the first 3 months of treatment (74% in KRYSTEXXA-treated patients vs. 51% in placebo-treated patients), and seemed to decrease over the next 3 months (41% KRYSTEXXA vs. 67% placebo). An increase in gout flares is frequently observed upon initiation of anti-hyperuremic therapy. Thus, all patients in these studies received non-steroidal anti-inflammatory drugs (NSAID) or colchicine or both for at least 7 days as gout flare prophylaxis before beginning KRYSTEXXA; patients continued on this regimen for the 6-month treatment duration.

All patients in Phase 3 clinical trials were pre-treated with an oral antihistamine (fexofenadine, 60 mg by mouth [po], the night before and morning of the infusion), i.v. corticosteroid (200 mg hydrocortisone i.v.) and acetaminophen (1000 mg po) before the infusion to prevent anaphylaxis and IRs. Nevertheless, IRs were reported in 26% of patients treated with KRYSTEXXA 8 mg every 2 weeks compared to 5% of patients treated with placebo. Manifestations of IRs included urticaria, dyspnea, chest discomfort, chest pain, erythema, and pruritus. Approximately 3% of IRs occurred with the first dose, and most (91%) occurred during the infusion rather than after it was completed.

None of the IRs which occurred in the pegloticase studies was categorized as anaphylaxis by the investigators who enrolled subjects in the Phase 2, Phase 3, or open-label extension studies. The US FDA performed a retrospective analysis of the IRs to assess for anaphylaxis, using modified National Institute of Allergy and Infectious Disease/Food Allergy and Anaphylaxis Network (NIAID/FAAN) diagnostic criteria (Sampson et al, 2006). Using their analysis, the frequency of anaphylaxis was 6.5% in all patients treated with KRYSTEXXA 8 mg every 2 week. During randomized, placebo-controlled studies, the frequency was 5% compared to none with placebo. An independent immunologist commissioned by the sponsor to review the data based strictly upon the NIAID/FAAN clinical criteria for anaphylaxis determined the overall rate in the clinical studies to be 2.4%.

A retrospective analysis of the data from the Phase 3 trials revealed that most IRs occurred when uric acid values were above 6 mg/dL. Importantly, other than one case that met the criteria for anaphylaxis occurring during the first dose of pegloticase (8 mg), all other cases that met the criteria for anaphylaxis occurred when a subject's last uric acid value was above 6 mg/dL. Thus, the monitoring rule was developed and incorporated into the FDA-approved Full Prescribing Information:

“Monitor serum uric acid levels prior to infusions and consider discontinuing treatment if levels increase to above 6 mg/dL, particularly when 2 consecutive levels above 6 mg/dL are observed.”

Other non-serious AEs reported in  $\geq 5\%$  of patients treated with KRYSTEXXA 8 mg every 2 weeks included nausea (12%), contusion or ecchymosis (11%), nasopharyngitis (7%), constipation (6%), chest pain (6%) and vomiting (5%).

Anti-pegloticase antibodies developed in 92% of patients treated with KRYSTEXXA. High anti-pegloticase antibody titers ( $> 1:2430$ ) were associated with both a failure to maintain pegloticase-induced normalization of uric acid and a higher incidence of IRs. Because of this high rate of antibody development, one of the specific safety endpoints in the larger population for the current study will be to determine if there is a risk of immune complex disease in patients treated with KRYSTEXXA. No cases of immune complex disease were identified in the pre-marketing controlled clinical studies.

While KRYSTEXXA has not been formally studied in patients with congestive heart failure, there were some patients who experienced exacerbation during the clinical studies. It was

therefore recommended that treating physicians exercise caution when using KRYSTEXXA in patients who have congestive heart failure and to monitor patients closely following infusion.

Glucose-6-phosphate dehydrogenase (G6PD) deficiency is a contraindication for KRYSTEXXA due to the risk of hemolysis and methemoglobinemia in these patients. Therefore, all patients in this study must be screened for this enzyme deficiency.

Refer to the current version of the FDA-approved KRYSTEXXA Full Prescribing Information and Pegloticase Investigators Brochure for detailed information concerning the safety profile of KRYSTEXXA.

### **1.3 Study Rationale**

This Phase 4, observational study is primarily focused on evaluating the frequency and severity of IRs, anaphylaxis, and immune complex-related AEs in adult patients with chronic gout refractory to conventional therapy who are being treated with KRYSTEXXA. In the post-approval setting, this study also provides a means of identifying and assessing any SAEs associated with KRYSTEXXA therapy. The efficacy of KRYSTEXXA, in terms of normalizing SUA and decreasing the number of swollen joints and tender joints, reducing gout flares, and resolving tophi in this patient population can also be further evaluated in a large population within the standard healthcare setting.

## **2 STUDY OBJECTIVES**

### **2.1 Primary**

The primary objective of the study is to evaluate the frequency and severity of IRs, anaphylaxis, and immune complex-related events.

### **2.2 Secondary**

Secondary objectives are to identify SAEs associated with KRYSTEXXA therapy and to further evaluate the efficacy of KRYSTEXXA in this patient population of adult hyperuricemic patients with gout refractory to conventional therapy.

## **3 INVESTIGATIONAL PLAN**

### **3.1 Overall Study Design**

[figure not shown]
This is a Phase 4, multicenter, open-label, single-arm observational study of KRYSTEXXA 8 mg i.v. every 2 weeks in adult hyperuricemic patients with gout refractory to conventional therapy. Approximately 1500 patients will be enrolled in order to observe treatment of up to 500 patients at approximately 300 centers in the United States (US). Study duration is approximately 63 weeks, including 51 weeks of treatment and 12 weeks of follow-up. Patients who discontinue treatment before 51 weeks (i.e., before all 26 planned KRYSTEXXA infusions) will be asked to remain in the study for follow-up assessments for the remainder of their planned treatment duration. It is estimated that approximately 2.5 years will be required for recruitment, from the

first to the last patient's screening visit. The number of patients to be enrolled will be reassessed approximately 2 years after the first patient is enrolled.

Patients not already on a prophylactic regimen of colchicine or NSAID to prevent gout flares should be placed on one of these agents at the time of study entry, unless medically contraindicated (see Section 3.5.7.1). All patients will receive KRYSTEXXA 8 mg i.v. every 2 weeks, admixed in 250 mL of 0.45% or 0.9% Sodium Chloride Injection, USP for i.v. infusion over a target infusion time of 120 minutes. Standardized infusion reaction prophylaxis consisting of pre-treatment with antihistamines and corticosteroids will accompany each infusion (see Section 3.5.8.1). The drug name, dose and timing of these prophylactic medications will be recorded.

A schematic diagram of the study design appears in Figure 1, and the Schedule of Procedures and Evaluations is located in Appendix 3.

**Figure 1** Study Design

### **3.2 Discussion of Design**

The primary objective of this Phase 4, observational study is to further evaluate the frequency and severity of IRs, anaphylaxis, and immune complex-related events in patients receiving treatment with KRYSTEXXA. Anaphylaxis and IRs were frequently reported (> 5% of subjects) AEs in the pivotal Phase 3 studies involving KRYSTEXXA, and immune complex-related AEs are a concern with any biological agents (Chen, 2010). For this study, the following will apply:

- IRs will be defined as any AE or cluster of AEs, not attributable to another cause, that occurs during or within 2 hours after the infusion of KRYSTEXXA. Other cases that occur outside of the 2-hour window may also be categorized as an IR as per investigator discretion.
- Anaphylaxis will be defined using the NIAID/FANN criteria (Sampson et al, 2006), comprised of involvement of the skin or mucosal tissue and either respiratory compromise or reduced blood pressure or associated symptoms of end-organ dysfunction (refer to Table 1). Mast cell involvement in any constellation of signs and symptoms will be evaluated by measuring serum tryptase levels.
- Immune complex-related AEs will be defined as any presumptive immune complex-related disorders that are confirmed by an appropriate investigation of the disease and of complement markers (complement component 3 [C3], complement component 4 [C4]). Clinical manifestations could include skin rash, arthralgia, arthritis, and proteinuria (see Section 3.8.1.3).

The proposed patient number (approximately 1500 enrolled patients in order to observe treatment of up to 500 patients for a duration of 1 year) and 1-year duration of the study will significantly extend the patient exposure to KRYSTEXXA compared with the pre-marketing controlled clinical trials.

In addition, post-hoc analyses of the clinical study data demonstrated that if KRYSTEXXA had been stopped when a patient's uric acid level rose to greater than 6 mg/dL at 2 consecutive visits, the incidence of IRs would have been reduced by half and there would have been little change in the efficacy outcome. Current guidance for the use of KRYSTEXXA thus recommends monitoring SUA levels prior to infusions and considering discontinuing treatment if SUA levels increase to above 6 mg/dL, particularly when 2 consecutive levels above 6 mg/dL are observed. This study will follow this guidance and provides for the collection of data on both SUA levels and IRs to extend the knowledge base regarding the relationship between these factors.

The design of this study follows the FDA-approved Full Prescribing Information for the use of KRYSTEXXA and allows for capturing additional data related to the safety and efficacy of KRYSTEXXA within the standard healthcare setting. Efforts have been made to limit study-specific activities for the enrolled patients and participating healthcare providers while still allowing for a robust assessment of key safety and efficacy features of KRYSTEXXA treatment in this patient population.

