#### **3.5.8.1 Infusion Reaction Prophylaxis**

Infusion reactions are not uncommon when biological agents are administered by i.v. infusion. Therefore, all patients will receive pre-treatment prophylaxis consisting of at least an antihistamine and corticosteroid prior to each infusion of KRYSTEXXA. In order to standardize this regimen, patients will use 60 mg fexofenadine po the night before and the morning of the infusion and 200 mg hydrocortisone iv before the infusion. If the investigator feels this regimen is not appropriate for an individual patient, s/he should contact the medical monitor to discuss alternative therapy. The name, dose and time of administration of each prophylactic medication will be recorded in the medical record and in the CRF/eCRF.

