#### **6.1.6 Safety Evaluation**

Adverse events will be summarized by presenting the proportion of patients having any AE, overall and by body system, and by event as defined by the MedDRA preferred term. Separate summary tables will be provided for IRs, anaphylaxis AEs, and immune complex-related AEs.

For each type of the primary safety endpoints, one event, at most, will be counted per patient. The 95% (exact) confidence interval estimates for each type of safety endpoint will be reported for the rate of incidence at the final analysis. The following hypothesis will be specifically tested: the rate of IRs seen in the Phase 3 studies will be reduced in this study by monitoring SUA prior to infusions and discontinuing therapy if levels increase to above 6 mg/dL, particularly when 2 consecutive levels above 6 mg/dL are observed. With at least 500 patients enrolled with 1 year follow-up, the power of detecting a 26% IR rate (the observed value from the pre-approval Phase 3 studies) against 13% is at least 90%. The rate of IRs reported during the study will be reported and compared descriptively to the rates observed in the pre-approval Phase 3 studies.

Descriptive statistics for laboratory values, vital signs, and their changes from baseline will be provided. Safety data will be listed as appropriate. Further details will be specified in the SAP.

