#### **Report Format/Structure**

- Enrollment
  - What has been done to address enrollment over the years?
  - o Number of patients enrolled per calendar year?
  - o Number of sites recruited for study since study initiation
    - Number of actively enrolling sites
      - Number of actively enrolling sites per calendar year
    - Number of sites dropping out per year
    - Reason for site drop outs
- Safety Endpoints
  - O Number of IRs by dose (1st v. 2nd v. 3rd etc.)
  - o IRs by severity or not by dose
  - O Number of anaphylaxis by dose (1st v. 2nd v. 3rd etc.)
  - o Anaphylaxis severity or not by dose
- Efficacy endpoints
  - o Number of patients meeting the primary efficacy effect at 24 and 52 weeks
  - o Number of protocol treated patients meeting the primary efficacy effect
- 1. Patient disposition flow chart:
  - a. Total Number of patients screened
  - b. Number of patients dosed
    - i. Number of patients currently receiving drug
  - c. Number of completers at 24 weeks
    - i. How many were responders versus non responders (based on primary efficacy criteria)
  - d. Number of completers at 52 weeks
    - i. How many were responders versus non responders (based on primary efficacy criteria)
  - e. Number of non-completers at 24 and 52 weeks
    - i. Reason for non-completing (AE, IR, etc.)
  - f. Number of patients treated per protocol through 24 and 52 weeks
    - i. Chart out responders versus non-responders in this cohort
- 2. Dosing:
  - a. Total number of infusions by study cut-off

- b. Total number of infusions per patient
- c. Number of IRs per total number of infusions
- 3. Protocol violations related to time SUA measured before pegloticase infusion
  - a. Number of times SUA was over 6
  - b. Number of patients who continued to receive infusion after SUA > 6 on 2 consecutive occasions in 24 and 52 week cohorts
  - c. Number of patients with premature (> 48 hours before infusion) SUA measures with AE, SAE (IRs, anaphylaxis).
- 4. Protocol violations related to dosing (schedule other than Q2 week dosing)
  - a. Number of patients with dosing violations with AE, SAE (IRs, anaphylaxis).
- 5. Number of patients in follow up
  - a. Reasons for loss to follow-up? (AEs, SAEs, death, etc.)
- 6. How would protocol be amended to encourage enrollment, study compliance, and significantly less number of completers (200) versus the original protocol (500)?

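### The infusion-reaction test credits any fall below 26% to SUA monitoring, but a single arm against a fixed Phase 3 rate cannot support that, and no analysis of reactions by pre-infusion SUA level is planned

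*Protocol*

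**What the plan says.** Protocol 3.1 describes a "multicenter, open-label, single-arm observational study". Protocol 6.1.6 states one hypothesis for testing: "the rate of IRs seen in the Phase 3 studies will be reduced in this study by monitoring SUA prior to infusions", together with stopping therapy when SUA rises. At most one event per patient is counted for each primary safety endpoint. The power statement assumes 500 or more patients observed for one year and claims that "the power of detecting a 26% IR rate (the observed value from the pre-approval Phase 3 studies) against 13% is at least 90" percent. The paragraph ends by saying that the IR rate will be compared descriptively with Phase 3.

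Protocol 3.2 says that the study "provides for the collection of data on both SUA levels and IRs to extend the knowledge base regarding the relationship between these factors". This relationship is not among the objectives in Protocol 2.1 and 2.2 or in the SAP.

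On premedication, Protocol 1.2.2 reports that Phase 3 patients received fexofenadine plus "i.v. corticosteroid (200 mg hydrocortisone i.v.) and acetaminophen (1000 mg po) before the infusion". For this study Protocol 3.5.8.1 says "patients will use 60 mg fexofenadine po the night before and the morning of the infusion and 200 mg hydrocortisone iv before the infusion". It presents an antihistamine and a corticosteroid as a minimum and allows alternatives after discussion with the medical monitor.

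The SAP (Report Format/Structure) contains no hypothesis test. It lists IRs by dose number, by severity and as "Number of IRs per total number of infusions". Its SUA items are:
- 3a: how often SUA was over 6.
- 3b: patients who kept receiving infusions after two consecutive values above 6.
- 3c: patients whose SUA was drawn more than 48 hours before infusion and who had adverse events, including IRs.

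**The concern.** The hypothesis names a cause, SUA monitoring with stopping, but the comparison has no element that isolates it. Everything that differs between this study and Phase 3 enters the contrast with 26%. A low rate could be credited to monitoring when something else produced it, and a rate near 26% could be read as failure when monitoring had worked.

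The rule rests on retrospective and post-hoc Phase 3 analyses (Protocol 1.2.2 and 3.2). This study records SUA around each infusion, infusion times, premedication, and IR onset relative to the infusion. It could therefore examine prospectively whether IRs cluster above 6 mg/dL, yet no planned output does so.

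**Working it through.** **1. The plan's own power figure.** Inputs from Protocol 6.1.6: p0 = 0.26, p1 = 0.13, n = 500. Alpha is not stated; I assume two-sided 0.05, to match the 95% intervals, and treat 26% as fixed.

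Power = Φ[(|p0 − p1|√n − 1.96√(p0(1 − p0))) / √(p1(1 − p1))]
= Φ[(0.13 × 22.36 − 1.96 × 0.4386) / 0.3363]
= Φ(6.09), above 0.9999.

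The claim of at least 90% reproduces. By this formula 90% needs only about 99 patients (about 109 by the exact test). At 200 patients, the number of 24-week completers that the SAP raises, power is 0.998 (exact 0.996). Sample size is not the difficulty.

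**2. Rejection when monitoring does nothing.** The exact binomial test of 26% at one-sided 0.025 with n = 500 rejects at 110 or fewer patients with an IR (110/500 = 22.0%; actual size 0.022). Suppose other differences alone set the true rate:

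| True rate | P(reject), n = 500 |
|---|---|
| 24% | 0.16 |
| 22% | 0.53 |
| 21% | 0.73 |
| 20% | 0.88 |

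More patients make this worse. At n = 1500 the limit is 356 (23.7%), and a true rate of 22% rejects with probability 0.95.

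**3. Non-rejection when monitoring works.** The placebo-controlled Phase 3 studies lasted 6 months (Protocol 1.2.1); treatment here runs 51 weeks (Protocol 3.1). With one event at most per patient, the proportion can only grow with time. Assume a constant hazard:
- No effect: 1 − 0.74² = 45.2% at 12 months.
- Hazard halved: 1 − 0.74^(2 × 0.5) = 26.0% at 12 months. P(reject) = 0.022.
- The 6-month proportion halved to 13%, then the same hazard: 1 − 0.87² = 24.3%, still above the 22.0% limit.

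The documents do not give the hazard's shape. If IRs come mostly early, or patients at risk stop early, the 12-month proportion lies closer to the 6-month one and this bias shrinks.

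**4. Documented differences from Phase 3 other than SUA monitoring.**

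| Feature | Phase 3 | This study |
|---|---|---|
| Duration | 6 months | 51 weeks |
| Setting | Randomized, double-blind | Open-label, standard healthcare |
| Fexofenadine and hydrocortisone | 60 mg twice; 200 mg i.v. | Same |
| Acetaminophen | 1000 mg | Not listed |

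**5. Material for a within-study analysis.** Assume constant discontinuation leaving 500 of 1500 patients on drug at Visit 26: h = ln(3)/50 per week. The sum of exp(−2hk) for k = 0 to 25 is 15.84 infusions per patient. Then 15.84 × 1500 = 23,760 infusions, or 22,260 after the 1500 at Visit 1. If each of up to 1000 patients who stop had 0 to 2 infusions above 6 mg/dL, that group would hold 0 to 2000 infusions. The range includes zero, so informativeness is not guaranteed.

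**The case against.** Several points on the other side stand.

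- A reader might infer that the SUA–IR relationship is a study objective. It is not listed as one; Protocol 3.2 promises data collection. The causal wording that matters is in the 6.1.6 hypothesis.
- A reader might infer that Phase 3 used a different premedication regimen. The antihistamine and steroid match in drug and dose. Acetaminophen is unlisted but not prohibited, and premedication taken is recorded. Actual use is unknown, and the documents give no size or direction for any effect. Duration is the clearer mismatch.
- A reader might infer that the SAP never connects SUA with IRs. Item 3c does, but through sample timing and not SUA level; item 3b measures adherence to the stopping rule.
- The protocol already says the comparison is descriptive. That helps only partly, because the same paragraph also states a test with power.
- A within-study contrast is not causal either. Infusions above 6 mg/dL occur before a second high value, after an interruption (Protocol 3.5.5), or when the rule is not followed. High antibody titers are linked both to loss of urate control and to IRs (Protocol 1.2.2). This stands in full and limits what the added analysis may claim.

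**Conclusion.** The concern holds in this form: the planned comparison cannot attribute a change in the IR rate to SUA monitoring, and the plan omits the analysis that its own data allow, IRs by pre-infusion SUA level. The error can run either way. At n = 500, unrelated differences giving a true rate of 20% to 22% would reject with probability 0.88 to 0.53; a true halving of the hazard would reject about 2% of the time. These figures rest on an exact one-sided 0.025 test with 26% taken as fixed. The second also needs a constant hazard, so it illustrates the effect of duration and is not a forecast.

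The documents do not support concluding that the study is underpowered for its stated contrast, that the acetaminophen difference explains any result, or that a contrast by SUA level would prove that monitoring lowers IRs.

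**What to change.** 1. In Protocol 6.1.6 and the SAP's Safety Endpoints, add an infusion-level table and model for infusions after Visit 1. Report IRs and adjudicated anaphylaxis by last pre-infusion SUA: 6 mg/dL or below; first value above 6; second or later consecutive value above 6; not available. Use patient-clustered confidence intervals and adjust for dose number and recorded premedication, including acetaminophen. Label the result associational, because the stopping rule selects which infusions take place above 6 mg/dL.
2. Define the SUA exposure. Protocol 3.5.2.1 suggests a confirmatory redraw, so two values may precede one infusion; state how that is classed. Protocol 3.6.1 has blood taken several days before infusion, while SAP item 3c treats more than 48 hours as premature. These must be reconciled.
3. Report a 6-month cumulative IR proportion to match the Phase 3 duration. Reword 6.1.6, and the matching synopsis text, so that the comparison with 26% is descriptive and non-causal and names the follow-up, setting and acetaminophen differences.

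Cost: wording, an exposure definition, and one table and model on data already collected. The downsides are a little more analysis, possibly few infusions above 6 mg/dL and so wide intervals, and a weaker claim from the historical comparison.
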